**Statement of Compliance**

This study will be conducted in accordance with the Code of Federal Regulations on the Protection of Human Subjects (45 CFR Part 46), 21 CFR Parts 50, 56, 312, and 812 as applicable, any other applicable US government research regulations, and institutional research policies and procedures. The International Conference on Harmonisation ("ICH") Guideline for Good Clinical Practice ("GCP") (sometimes referred to as "ICH-GCP" or "E6") will be applied only to the extent that it is compatible with FDA and DHHS regulations. The Principal Investigator will assure that no deviation from, or changes to the protocol will take place without prior agreement from the sponsor and documented approval from the Institutional Review Board (IRB), except where necessary to eliminate an immediate hazard(s) to the trial participants. All personnel involved in the conduct of this study have completed Human Subjects Protection Training.

**List of Abbreviations**

AE	Adverse Event/Adverse Experience
ASA	American Society of Anesthesiologists
BCPQ	Breast Cancer Pain Questionnaire
BMI	Body Mass Index
BPI	Brief Pain Inventory
CFR	Code of Federal Regulations
CIMU	Conflict of Interest Management Unit
CTO	Clinical Trials Office
CRF	Case Report Forms
DCC	Data Coordinating Center
DHHS	Department of Health and Human Services
DSMC	Data and Safety Monitoring Committee
eCRF	Electronic Case Report Form
ED	Emergency Department
FDA	Food and Drug Administration
GAD-2	Generalized Anxiety Disorder-2
GCP	Good Clinical Practice
GLP	Good Laboratory Practices
GMP	Good Manufacturing Practices
HIPAA	Health Insurance Portability and Accountability Act
HSR	Human Subject Research
ICF	Informed Consent Form
IEC	Independent Ethics Committee
ICH	International Conference on Harmonisation
IRB	Institutional Review Board
IV	Intravenously
MOP	Manual of Procedures
MRN	Medical Record Number
N	Number (typically refers to participants)
NIH	National Institutes of Health
OHRP	Office for Human Research Protections
NYU	New York University
NYULH	New York University Langone Health

**CONFIDENTIAL**

This material is the property of the NYU School of Medicine and Langone Medical Center. Do not disclose or use except as authorized in writing by the study sponsor

---

OR	Operating Room
PACU	Post Anesthesia Care Unit
PCC	Perlmutter Cancer Center
PHI	Protected Health Information
PHQ-2	Patient Health Questionnaire-2
PI	Principal Investigator
POD	Postoperative Day
PROMIS	Patient-Reported Outcomes Measurement Information System
QC	Quality Control
QoR-15	Quality of Recovery
REDCap	Research Electronic Data Capture
SAE	Serious Adverse Event/Serious Adverse Experience
SAP	Statistical and Analytical Plan
SOP	Standard Operating Procedure
Sub-I	Sub-Investigator
TP	Treating Physician
UP	Unanticipated Problems
US	United States

## Protocol Summary

Title	Randomized, single-blind, placebo-controlled study on the effect of postoperative administration of single dose ketamine after mastectomy on pain
Short Title	Effect of postoperative single dose of ketamine on pain after mastectomy
Brief Summary	This is a randomized, single blinded, placebo-controlled trial to study the effectiveness of a subanesthetic dose (0.6mg/kg) of ketamine versus placebo (saline) on postoperative pain on adult women undergoing mastectomy.
Objectives	To examine the effect of a subanesthetic dose (0.6mg/kg) of ketamine vs. saline control on postoperative pain in subjects who have undergone mastectomy.
Methodology	Randomized, single blinded, placebo-controlled trial
Study Duration	Approximately 6 months
Participant Duration	7 days for 5 visits
Enrollment Period	Up to six weeks before surgery
Duration of Study Product Administration	At least 30 minutes at one time point
Population	Adults women, aged 18 to 80 years, who will undergo mastectomy
Number of participants	30 total participants (15 in treatment group, 15 in control group)
Description of Study Product (Ketamine) Administration	Ketamine[(+/-)-2-(2-chlorophenyl)-2-(methylamino)-cyclohexanone] is a white, crystalline powder or clear liquid. Ketamine at a dose of 0.6 mg/kg will be administered intravenously (IV) while the participant is recovering in the PACU. The study drug will be administered over at least 30 minutes at one time point and will be administered after subject has been deemed to be stable (hemodynamically stable, awake) by the study team on POD 0.
Reference Therapy	Saline. Saline is a prescription medicine used for fluid and electrolyte replenishment for intravenous administration. This is placebo drug in this study.
Key Procedures	IV administration of ketamine or saline Self-reported questionnaires Medical records review (opioid use and dosage assessments)
Statistical Analysis	Descriptive statistics will be used to summarize continuous variables. The normality of the distributions for continuous variables will be tested using Q-Q plots and Shapiro-Wilk tests. Differences between arms will be compared with two-sample t-test if outcome is normally distributed or with Wilcoxon's rank-sum test otherwise.

CONFIDENTIAL

This material is the property of the NYU School of Medicine and Langone Medical Center. Do not disclose or use except as authorized in writing by the study sponsor

**Schematic of Study Design**

CONFIDENTIAL

This material is the property of the NYU School of Medicine and Langone Medical Center. Do not disclose or use except as authorized in writing by the study sponsor

## 1 Introduction, Background Information and Scientific Rationale

Ketamine is an effective analgesic that can be administered pre-operatively, intra-operatively or postoperatively. Although pre-operative administration of a single bolus dose of ketamine prior to incision has shown mixed results, its use as a continuous infusion intra-operatively or postoperatively can reduce opioid consumption after surgery.

An alternative to ketamine infusion is single dose ketamine. Recently, ketamine has emerged as a powerful antidepressant and anxiolytic with enduring effects that can last a week. A single ketamine bolus (0.3-0.6mg/kg) can effectively activate the cortical top-down system for mood regulation. Single bolus ketamine has also been used in the emergency department (ED) to provide long-lasting post-discharge pain relief and minimize opioid prescriptions. In a recent pilot randomized controlled trial (RCT) of single-dose ketamine in the postoperative care unit (PACU), we found that ketamine reduced the affective component of pain for 7 days after bariatric surgery. This study utilized a ketamine dose of 0.4 mg/kg based on ideal body weight. In addition, patients had relatively low levels of baseline anxiety and depression. To ensure robust treatment effects in our current study, we have increased the effective dose to 0.6 mg/kg, which is in the range of the therapeutic dose for mood disorders and pain in the ED. We hypothesize that single bolus dose ketamine may potentially be more helpful in certain surgical populations with high baseline depression or anxiety.

Patients undergoing mastectomy for breast cancer have higher levels of depression and anxiety. Postmastectomy pain is associated with more postoperative pain than laparoscopic bariatric surgeries. We hypothesize that a single-dose (0.6 mg kg) administration of ketamine after surgery may be able to relieve postoperative pain, improve mood and postoperative recovery, and decrease opioid requirements in patients undergoing mastectomy.

Thirty subjects undergoing mastectomy will be randomized to receive a single-bolus ketamine (0.6mg/kg) administered after surgery in the post-anesthesia care unit (PACU) or placebo (saline) control. All subjects will receive standard of care routine postoperative multimodal analgesia throughout hospital stay and after discharge. The Brief Pain Inventory (BPI) pain severity score at 24h and 48h post-surgery will serve as the primary endpoint. Secondary endpoints include responses on BPI (pain severity and interference subscales), opioid use, Quality of Recovery (QoR-15), National Institute of Health (NIH) Patient-Reported Outcomes Measurement Information System (PROMIS) scales for fatigue and sleep, Patient Health Questionnaire-2 (PHQ-2), Generalized Anxiety Disorder-2 (GAD-2), and Breast Cancer Pain Questionnaire. Side effects will also be assessed.

### 1.1 Name and Description of the Study Drug and Placebo

Ketamine [(+/-)-2-(2-chlorophenyl)-2-(methylamino)-cyclohexanone] is a white, crystalline powder or clear liquid. It is a schedule III substance and is classified as a dissociative anesthetic. Ketamine is available as a racemic mixture with the S-(+)- isomer being more potent than the R-(-)- isomer. It is commercially supplied as the hydrochloride salt in 0.5 mg/mL and 5 mg/mL ketamine base equivalents. Clinically, it is commonly used as an anesthetic induction agent for diagnostic and surgical procedures prior to the administration of general anesthetics. It is also used as a low dose infusion for analgesia.

Ketamine is a FDA-approved general anesthetic and analgesic agent that has been safely used clinically over the last 50 years. For general anesthesia, the induction dose ranges from 1mg/kg to 4.5 mg/kg. At sub anesthetic doses (< 1mg/kg), ketamine is a potent analgesic with a clinically effective half-life of 45 min. It is also a powerful antidepressant and anxiolytic, as a single dose (0.3-0.6mg/kg) which can produce up to 14 days of mood stabilization.

Saline is a prescription medicine used for fluid and electrolyte replenishment for intravenous administration.

CONFIDENTIAL

This material is the property of the NYU School of Medicine and Langone Medical Center. Do not disclose or use except as authorized in writing by the study sponsor

### **1.1.1 Clinical Data to Date**

#### **1.2 Rationale**

Ketamine is known to have analgesic effects as well as mood elevating effects. Ketamine is often administered as a continuous infusion. However, single doses have also been used and are simpler to implement. In previous studies for depression and pain, a dose range of 0.3-0.6 mg/kg was used. In our prior study of ketamine for bariatric surgery, we used 0.4 mg/kg for ideal body weight. To further evaluate a single dose of ketamine for postoperative pain, we will use 0.6 mg/kg, which is in the range of the therapeutic dose for mood disorders and pain. We hypothesize that postoperative use of ketamine can lead to improvement in pain indices including BPI, a decrease in opioid requirement, and mood improvements as measured by psychometric indices in subjects undergoing mastectomy surgery, a population with typically high baseline depression or anxiety.

#### **1.3 Known Potential Risks**

The risks for ketamine are well studied. In general, ketamine is a well-tolerated medication. There may also be risks that are currently unforeseeable.

**Psychological Effects:** Decreased awareness of general environment, sedation, dream-like state, vivid dreams, feelings of invulnerability, increased distractibility, disorientation, and subjects may be generally uncommunicative. Additionally, hallucinations, impaired thought processes, delirium, out-of-body experiences, and changes in perception about body, surroundings, time and sounds can occur. Emergence reactions have occurred in approximately 12 percent of subjects.

**Physiological:** Anesthesia, cataplexy, immobility, tachycardia, increased blood pressure, nystagmus, hypersalivation, increased urinary output, profound insensitivity to pain, amnesia, slurred speech, and lack of coordination.

**Cardiovascular:** Cardiovascular side effects have included elevated blood pressure and heart rate following administration of ketamine alone. However, hypotension and bradycardia have been observed. Other arrhythmias such as ventricular tachycardia are rare.

**Respiratory:** Respiratory side effects have included stimulated respiration, although severe depression of respiration or apnea may occur following rapid intravenous administration of ketamine. Laryngospasms and other forms of airway obstruction have occurred during ketamine anesthesia. Additionally, hypersalivation or the increased production of salivary and tracheobronchial secretions may occur, which may be clinically significant during extubation or post-op airway protection.

**Ocular:** Ocular side effects have included diplopia, nystagmus, and a slight elevation in intraocular pressure.

**Oral:** Hypersalivation or increased salivary secretions can occur during ketamine administration.

**Gastrointestinal:** Gastrointestinal side effects have included anorexia, nausea, and vomiting. It is possible that severe nausea and vomiting may occur during the post-op period due to the dual effects of the recent general anesthetic and ketamine administration.

**Musculoskeletal:** Musculoskeletal side effects have included enhanced skeletal muscle tone manifested by tonic and tonic movements sometimes resembling seizures.

**Local:** Local side effects have included pain and exanthema at the injection site.

**Dermatologic:** Dermatologic side effects have included transient erythema and/or morbilliform rash.

**Psychiatric:** Psychiatric side effects have included anxiety, euphoria, dysphoria, illusions, hallucinations, flashbacks, blunted affect, catatonia and psychotic episodes.

CONFIDENTIAL

This material is the property of the NYU School of Medicine and Langone Medical Center. Do not disclose or use except as authorized in writing by the study sponsor

**Neurologic:** Impaired attention/memory/judgment, disorientation, delirium, diplopia, and blurred vision.

**Urinary:** Increased urinary output; rarely cystitis.

**Duration of Effects:** Onset of analgesic effect of ketamine is within 1-5 minutes if injected. The effects of ketamine generally last 30-45 minutes if injected as a single bolus. However, some residual symptoms such as nausea and vomiting may persist longer than general effects.

**Drug Interactions:** Benzodiazepines may decrease ketamine-associated emotional distress but does not decrease cognitive or behavioral effects of ketamine. Acute administration of diazepam increases the half-life of ketamine. Lamotrigine significantly decreases ketamine-induced perceptual abnormalities but increases the mood elevating effects. Haloperidol may decrease impairment by ketamine in executive control functions, but does not affect psychosis, perceptual changes, negative schizophrenic-like symptoms, or euphoria. Alfentanil is additive to ketamine in decreasing pain and increasing cognitive impairment. Physostigmine and 4-aminopyridine can antagonize some pharmacodynamic effects of ketamine.

Contraindications include increased intracranial pressure (ICP), glaucoma, or acute globe injury. Caution is suggested in patients with cardiovascular illness, porphyria, or thyroid disorder.

Side effects typically end 30 minutes after the termination of infusion. These risks will be mitigated using the strategies described in the protection against risks and dose adjustments sections. There are no expected side effects associated with the administration of saline.

There are no known side effects associated with completing the questionnaires. There may be some mild level of fatigue associated with answering the questions.

**Confidentiality risks:** The risk is privacy violation via the unexpected release of protected health information through health records or research data or the release of randomization information. As a result, this study involves the possibility of psychological and social risks related to breach of confidentiality.

### **1.3.1 Protection against Risks**

Given that ketamine will be given in the recovery room, all participants will be monitored by the study care team and PACU physicians, if any of these effects mentioned above were to occur. For the risks of physiological effects and cardiovascular side effects, the single bolus ketamine dose will be given over at least a 30-minute period to minimize these effects from happening. For the risks of psychomimetic side effects, such side effects may be treated with reassurance.

The investigators have many layers of protection to minimize the risk of inadvertent release of protected health information. The methods for de-identification of data will mitigate this risk. We will take all necessary precautions to maintain complete confidentiality of data and prevent unauthorized access to the data. Data will only be collected from subjects who consent and whose physicians deem safe to proceed with data collection. Participants will be allowed to exit the study at any time. Participants who withdraw consent will be counseled that their withdrawal only affects uses and sharing of information after their written request to withdraw authorization has been received, and that their authorization may not be withdrawn for uses or disclosures that have previously made or need to be made to complete analyses or report data from the research. For the confidentiality of randomization, only the physician administering the study drug will know which group the subject(s) is/are in for the both experimental and control group.

All data and records generated during this study will be kept confidential in accordance with institutional policies and HIPAA on subject privacy. The study investigators will not use such data and records for any other purpose other than conducting the study. Privacy protection procedures are in place and good clinical practice guidelines will be followed throughout the study to minimize the risks associated with breach of confidentiality. This risk will be minimized by strict compliance with HIPAA procedures for securing PHI.

CONFIDENTIAL

This material is the property of the NYU School of Medicine and Langone Medical Center. Do not disclose or use except as authorized in writing by the study sponsor

Information that could be used to identify the subject will only be shared with researchers who have approval of the IRB.

#### **1.4 Known Potential Benefits**

Perioperative ketamine improves pain and reduces opioid use in the acute postoperative period. Additionally, other benefits may include a reduction in depression and anxiety symptoms and improvements on long-term pain management and function. There is a potential benefit gained to study subjects for better postoperative analgesia and mood elevation as well as faster recovery from surgery. There is also a potential for longer term benefit on the affective component of pain from the mood elevating effects of ketamine. In addition, there is benefit in society for better understanding of the postoperative analgesic and mood elevating strategies, physical function, sleep quality, and opioid use requirements. It is possible some present subjects will not benefit but future patients may benefit from this study. The information obtained from this research may help others in the future.

### **2 Objectives and Purpose**

Ketamine in the perioperative period is most frequently administered as an infusion. In our previous study of ketamine in bariatric surgery, we administered a single dose of 0.4 mg/kg in the recovery room and noted improvements in the affective component of pain. In this study, we will examine a single dose of ketamine at 0.6 mg/kg in the recovery room in patients undergoing mastectomy to obtain a preliminary assessment of efficacy for pain. Mood, sleep quality, function and opioid requirements will also be measured.

#### **2.1 Primary Objective**

The primary objective is to examine the effect of a sub anesthetic dose of (0.6mg/kg) of ketamine vs. saline control on postoperative pain in subjects who have undergone mastectomy.

#### **2.2 Secondary Objectives**

The secondary objective is to examine the effects of a sub anesthetic dose of (0.6mg/kg) of ketamine vs. saline control on pain interference, mood, recovery (sleep quality and physical function), and opioid use in patients who have undergone mastectomy. Incidence of side effects will also be evaluated through the psycho-behavioral questionnaire.

### **3 Study Design and Endpoints**

#### **3.1 Description of Study Design**

This is a randomized, single-blind, placebo-controlled, two-arm parallel, single-center study.

Thirty subjects (15 in each arm) will be accrued. Randomization lists will be sent only to the study physician administering study drug. Participant and assessor of outcome measures will be blinded. The surgeon, anesthesiologist, and the research team members conducting the follow up visits will not know which group the subjects are assigned to. The physician administering the study will be aware of whether ketamine or placebo is administered. On the day of the mastectomy surgery, the subject will be randomly assigned to the control or the experimental group.

Adult women who will be undergoing mastectomy will be screened for eligibility to participate in the study. Prospective subjects will be recruited, screened and consented prior to surgery. Eligible subjects will be randomized to one of the two groups in a 1:1 ratio to receive either intravenously (IV) ketamine (0.6mg/kg) or matching equal dose of placebo. Only women will be recruited in this study, as mastectomies are primarily done in women. As men represent less than 1% of breast cancer cases and mastectomy may have a different psychosocial impact on them, we will only enroll women for this study. There is no limitation as to racial and ethnic origin.

Participation in the study will not alter the subject's surgical or anesthetic care, post-anesthetic care, or standard of care on the floor. In the PACU, subjects, if deemed medically stable by the study physician, will receive equal dosage of 0.6mg/kg IV ketamine or saline placebo. All subjects will also receive standard post-anesthetic monitoring and care, as well as routine care after transfer out of the PACU. There is no restriction on the use of other analgesics throughout this study. Subjects are followed, and endpoints (see

CONFIDENTIAL

This material is the property of the NYU School of Medicine and Langone Medical Center. Do not disclose or use except as authorized in writing by the study sponsor

below) are collected from subject reports as well as from medical charts (opioid use). During the study, subjects will fill out self-reported questionnaires assessing pain, mood (fatigue) and function (physical), side effects, and quality of postsurgical recovery including sleep quality.

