### **5.1.4 Preparation**

Study drug is obtained from NYULH inpatient pharmacy [contact]). Study physician is not blinded. Ketamine will be diluted to 2-10 mg/ml in normal saline by study physician. 0.9% normal saline will be used as the control.

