### **5.1.6 Study Agent Accountability Procedures**

Study drug will be ordered by study physician when participant arrives to PACU. Regular study drug reconciliation will be performed to document drug assigned, drug consumed, and drug remaining. Controlled substance disposal procedures will be followed per pharmacy procedure.

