**6.1.2 Intermediate Visits****Study Visit 2 (Visit 2, Day 1, POD 0)**

- Perform randomization.
- Administer the study intervention, ketamine single dose or placebo. Administration of normal saline placebo is standard of care.
- BPI pain severity subscale, opioid use, and side effects (psycho-behavioral questionnaire) will be assessed in person after infusion.
- Record adverse events as reported by participant or observed by investigator and study team.

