### **9.2 Measures to Minimize Bias**

#### **9.2.1 Enrollment/Randomization/Masking Procedures**

The subjects will be randomized in a 1:1 ratio. The treatment subjects will receive 0.6 mg/kg of the study drug, and the control subjects will receive an equal volume of saline. Participants will be randomized with random size permuted blocks, blinded with respect to treatment assignments. [name] will generate the randomization list.

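### The randomization lists go to the unblinded physician who doses and judges PACU stability, with no described step that withholds upcoming assignments; separately, replacement is not limited to losses before randomization

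*Combined protocol and SAP*

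**What the plan says.** **Who holds the list and who judges stability.** Section 3.1 states "Randomization lists will be sent only to the study physician administering study drug". The same section says that, in the PACU, "subjects, if deemed medically stable by the study physician, will receive equal dosage". Section 5.1.4 adds "Study physician is not blinded". The Protocol Summary and section 5.1.5 describe the stability judgement differently: study drug "will be administered after subject has been deemed to be stable (hemodynamically stable, awake) by the study team on POD 0".

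**What limits knowledge of assignments.** Section 1.3.1 says "only the physician administering the study drug will know which group the subject(s) is/are in for the both experimental and control group". Section 9.2.1 says "Participants will be randomized with random size permuted blocks, blinded with respect to treatment assignments". Section 3.1 blinds participants, outcome assessors, the surgeon and the anesthesiologist.

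**Order of events on the day of surgery.** Section 6.1.2 lists "Perform randomization" first under Visit 2, then administration of the intervention. The schedule of events puts both in one row. Section 5.1.6 says "Study drug will be ordered by study physician when participant arrives to PACU".

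**Replacement and analysis.** Section 4.7.2 allows replacement of participants who withdraw or stop early, with no mention of whether the loss came before or after randomization. Section 4.7.1 keeps participants whose study drug was stopped in follow-up, if they consent. Section 4.6 expects about 50 enrolled to yield 30 evaluable, a term it does not define. Sections 10 and 10.1 name no analysis set. Section 9.1.1 expects to randomize 15 per arm.

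**The concern.** Randomization protects the comparison only if the person who decides whether a participant goes forward cannot know her arm when deciding. Here the recipient of the lists also has a part in the last decision before dosing. If upcoming assignments are visible and the decision comes before assignment, a borderline participant can be passed over, or not, according to her arm. She then never enters the randomized set. Blinding participants and assessors does not prevent this, because it acts afterwards.

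The replacement rule raises a different and smaller question. Several reasons in section 4.7.1 for stopping study drug are drug-related and could be more frequent with ketamine than with saline. If such participants were replaced and also left out of the analysis, the groups compared would no longer be the groups randomized.

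**Working it through.** **1. Does any visible text conceal upcoming assignments from the list holder?**

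- Section 1.3.1 restricts who knows the group. It does not say when that person learns it.
- Random-size blocks (section 9.2.1) make a hidden sequence harder to predict. They do nothing against someone holding the sequence.
- Eligibility is verified at Visit 1 (section 6.1.1). The stability judgement comes later, in the PACU.
- No visible section describes one-at-a-time release, sealed envelopes or a system that holds back the next assignment.

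**2. What follows under each order of events?**

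- Stability judged first, then assignment: a participant passed over is never randomized and cannot be recovered by any analysis.
- Assignment first, which the order in section 6.1.2 suggests: she is already randomized, and an analysis of all randomized participants keeps her.

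**3. Predictability.** Inputs: 30 participants, 1:1 (section 9.2.1). Assumed: the block sizes, which the documents do not give. Rule: guess the arm with fewer assignments so far and toss a coin at ties. Mean correct guesses by simulation:

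| Situation | Correct of 30 |
|---|---|
| List in hand | 30 |
| Hidden, one physician sees all; blocks 2/4 | 21.6 |
| same; blocks 2/4/6 | 21.0 |
| same; blocks 4/6 | 20.6 |
| same; blocks 4/6/8 | 20.2 |
| Hidden, two or three physicians, each recalling own cases only | about 16–17 |
| Chance | 15 |

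The row for several physicians matters because section 5.1.5.4 speaks of study physicians in the plural and section 4.6 names two hospitals.

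**4. The plan's own power figure.** Section 9.1.1: 15 per arm, effect 1.1 SD, two-sided alpha 0.05, Wilcoxon test, normal data, 80% power. The exact test gives 0.796, so the figure reproduces. The exact test's true two-sided level at 15 v 15 is 4.53%.

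**5. Replacement plus exclusion.** Assumed: some ketamine participants are replaced and left out, and their like remain in the saline arm. Bias = (share left out) × (excess pain in SD of those left out), towards ketamine:

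| Left out of 15 | Excess 0.5 SD | Excess 1 SD | Two-sided error |
|---|---|---|---|
| 1 | 1/15 × 0.5 = 0.033 | 1/15 × 1 = 0.067 | about 4.5–4.8% |
| 2 | 2/15 × 0.5 = 0.067 | 2/15 × 1 = 0.133 | 4.8–5.7% |
| 3 | 3/15 × 0.5 = 0.100 | 3/15 × 1 = 0.200 | 5.2–7.0% |

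If those left out would have had less pain, the bias is the same size against ketamine. Power at 1.1 then falls from 0.80 to 0.74 (0.067 SD), 0.69 (0.133 SD) or 0.62 (0.200 SD). Equal losses in both arms with the same excess pain cancel.

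The documents give no stopping rate. The nearest figure is emergence reactions in about 12% (section 1.3), which is 0.12 × 15 = 1.8 participants at any severity. Among psychomimetic effects, section 4.7.1 lists only severe ones as a reason to stop, and the other stopping reasons have no rate.

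**The case against.** **The release procedure may exist out of sight.** The study schematic is not shown in the available copy, and section 14.3 refers to a Manual of Procedures that is not included. Either could fix the order of events or describe single release. This stands: the order of assignment and stability check cannot be called unstated in the plan, and advance knowledge cannot be asserted.

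**The visible order is the benign one.** Section 6.1.2 lists randomization before dosing, eligibility is settled at Visit 1, and two of three descriptions give the stability judgement to the study team. No section says that a participant who is not yet stable is dropped. This also stands, and it lowers the likelihood of harm. It does not remove the point, because what section 3.1 describes is the sending of lists, not single release.

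**The replacement rule has a natural harmless reading.** It sits under withdrawal from the study, while section 4.7.1 separately keeps those who only stop drug. Replacement adds participants; no section removes anyone who has data. This largely stands. The remaining ambiguity is that section 4.7.1 speaks of discontinuation from treatment and also from the study.

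**Stronger readings that the documents do not support.** A reader might infer that the physician is given the complete sequence in advance; the text says neither that it is complete nor when it is sent. A reader might also infer that 20 of 50 participants are lost after randomization. Enrollment is at Visit 1, randomization at Visit 2, and section 9.1.1 expects 15 randomized per arm, so that loss may fall wholly before randomization.

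**Conclusion.** The point holds in a limited form and is worth fixing because the change is cheap. The main part rests on what section 3.1 states: the lists go to an unblinded physician who, in that section, also judges stability before dosing, and no visible text withholds upcoming assignments. Selection by arm is possible, not demonstrated. No outcome bias is estimated for it, because the documents give no basis. Hiding the list cuts correct prediction from 30 of 30 to roughly 16–22, depending on the assumed block sizes and on how many physicians share the cases; it does not reach chance.

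The replacement part is lesser. Bias needs participants to be both replaced and left out. On assumed shares and an assumed direction, error stays below 5% with 1 of 15 left out, and only the most extreme case (3 of 15, 1 SD more pain) reaches 7%. The undefined term in section 4.6 is a matter of clarification only. The 80% power statement is not in dispute. Nothing here says who should judge stability or when study drug should stop.

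**What to change.** **Main change, section 3.1.** Do not send the list. Release each assignment singly, after eligibility and PACU stability have been recorded, through REDCap randomization if available, or otherwise by sequential sealed envelopes prepared by someone who does not give study drug. Keep block sizes from the study physicians. Reconcile the Protocol Summary, sections 3.1, 5.1.5, 5.1.6 and 6.1.2 and the schedule of events with that order. Cost: wording, REDCap set-up or envelopes, and a short delay before drug preparation. This protects decisions before dosing only, not later decisions to stop.

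**Lesser change, sections 4.7.2 and 10.1.** Limit replacement to participants lost before randomization. Make the primary analysis all randomized participants as assigned, including those whose infusion was stopped and who continue visits. Reconcile this with section 4.7.2, which speaks both of destroying data after formal withdrawal and of telling participants whether earlier data will be kept and analysed, and with sections 1.3.1 and 13.5, which allow use of data already collected. The Wilcoxon comparison can include only participants with outcome data, so report those without, by arm. Cost: possibly fewer than 30 complete cases. Power at 1.1 would go from 0.80 to 0.78 (14 v 14), 0.77 (13 v 15) or 0.73 (13 v 13). If 30 with data are wanted, set the number randomized higher in advance, alike for both arms.

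**Clarification, section 4.6.** State the numbers consented and randomized separately, and define evaluable or drop the term.
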